- Patients undergoing medial foot, medial ankle, medial leg or knee surgery.
- Information from medical records including PHI, preoperative anesthesia report, intraoperative anesthesia report, post-operative notes, progress notes, Surgery transcript, and Acute Pain Service documentation.
- Performance of ACB for the purpose of postoperative pain
- Sensory mapping
- Evaluation of efficacy of postoperative analgesia

9. Recruitment Methods and Consenting Process:

Eligible subjects will be undergoing lower extremity surgery of the medial foot, ankle, leg or knee for which the anesthetic plan already includes an adductor canal block. Patients will be identified in the orthopedic presurgical clinic or preoperative anesthesia clinic, or by reviewing operating room master daily schedule in Epic. The patient chart will be reviewed in accordance with a HIPAA viewer authorization. Providers first proposing study participation will come into contact with patients during routine preoperative contact to ensure HIPAA compliance. Eligible patients will be approached by the anesthesia service or research coordinator/assistant within four weeks prior to surgery.

The purpose of the study and potential risks, benefits and complications of the study will be explained. Adequate time will be given to read the consent form. All questions will be answered before the patient is asked to sign the consent form. If the subject agrees to participate, written, informed consent will then be obtained using UTSW IRB-approved informed consent form and HIPAA consent form prior to any study procedures in the pre-operative period on the day of surgery or in the preanesthetic clinic.

10. Potential Risks:

There is minimal risk to subjects by participating in this study. Potential risks include loss of confidentiality or mild discomfort associated with the pinprick for sensory testing. There are no additional physical or psychological risks that may result from participation in this

research protocol since patients will have determined that they desire perineural blockade before study inclusion is even proposed.

- Risks of adductor canal blockade:

The needle may damage surrounding tissues, including nerves, and may cause bleeding and infection. Each of these is rare (<1%). There is a potential risk of local anesthetic toxicity; however, this too is rare (<1%). There is a theoretical increased risk of fall should local anesthetic spread to the motor nerves of the quadriceps other than the vastus medialis; however, studies have shown preserved quadriceps muscle function following ACB.

- Risk of Pinprick testing

There may be minimal discomfort during pinprick testing. Neuropen stimulation will be performed gently across the skin to decrease discomfort.

- Risk of MVIC testing

There may be minimal discomfort during knee extension with application of the handheld dynamometer.

- Risks to an Embryo, or Fetus

Females: A urine pregnancy test will be performed before the enrollment of any female study participants of childbearing age. Pregnant females will not participate in the study.

- Psychological Stress

Some of the questions that will be asked as a part of this study may make a participant feel uncomfortable.

- Loss of Confidentiality

Any time information is collected; there is a potential risk of loss of confidentiality. Every effort will be made to keep patient information confidential.

11. Subject Safety and Data Monitoring:

Any serious adverse reaction, including allergy and local anesthetic systemic toxicity, will result in immediate discontinuation of study related procedures and treatment as necessary. Serious adverse events will be reported to the Institutional Review Board. The data already obtained from a participant who has had a serious adverse event will be analyzed according to intention-to-treat principle.

All data will be collected under the supervision of the primary investigator.

12. Procedures to Maintain Confidentiality:

All patients will be identified by a numerical code such as Case 01, Case 02, Case 03...etc. This code will be used during gathering and reporting the information. Direct patient identifiers

will not be used during data analysis. A key coding system will be created. De-identified study data will be recorded using the secure Redcap database.

Stored electronic data that contains PHI and/or other types of identifiable data will be encrypted and password protected and stored on a secure server. Subject identifiers will not be reused or disclosed to any other person or entity for research unless required by law, for authorized conduct and oversight of the study, or for other IRB-approved research.

All protected health information will be kept in a secure location with limited access.

Following the completion of the analysis and the project, the key to the coding system will be destroyed by shredding the documents so that there is no direct or indirect link to subject identifiers and information.

13. Potential Benefits:

Potential benefits in determining whether the two neurosensory blockade techniques are different include identifying a potential difference in the area of sensory blockade of the thigh, a potential difference in strength as indicated by MVIC, as well as suggesting a potential improvement in analgesia of the thigh and subsequent increase in patient satisfaction, as well as decreased postoperative opioid usage for future patients.

Both neurosensory blockade techniques are very safe, have little or no pain associated with administration, and have the same cost.

14. Biostatistics:

Sample Size Estimation:

There is no prior study to provide basis for a sample size estimation. Thus the study is powered to achieve 70% power with two-sided alpha = 0.05 for testing the equivalence of the two blocking methods. With an equivalence margin of 2 points (two blocking methods will be equivalent if mean score for one blocking method within two points of the other) and assuming a standard deviation of 3 points, the study will have 70% power with n = 34 in each group (total n = 68).

Statistical analyses:

Data will be summarized as mean and standard deviation for continuous variables and frequency and percentages for categorical variables. The equivalence of the two blocking methods will be tested using the two-one-sided-tests (TOST) procedure following Schuirmann (1987).²⁸ Pain scores and opiate consumption will also be analyzed in subgroups according to the location and type of surgery (foot vs. ankle vs. leg) and presence of concurrent sciatic block.

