A research assistant who is blinded to ACB approach will record the time taken to perform the block as defined as the time from the start of local anesthetic infiltration of the skin to the time the block needle was removed from the patient (Block performance time).

At the end of block performance a stopwatch will be started. Pinprick sensation and MVIC will occur at 20 minutes after block completion.

The efficacy of postoperative analgesia will be evaluated by using a 0-10 Likert scale (0=no pain, 10= worst imaginable pain). Pain will be evaluated in the PACU within 1 h postoperatively and postoperative Day 1 (POD1). If the patient is discharged to home, a phone interview will be performed within 24 h following the surgery for evaluation of POD1 pain scores, patient satisfaction, and monitoring adverse events.

Patient satisfaction as a measure of quality of pain management will be assessed POD1 via phone call on the scale of 1 to 5 (Poor=1, Fair=2, Good=3 Very good=4, Excellent=5).

The duration of the study period is 24 hours. Although participants will be participating in a research protocol, their clinical care will be the standard of care as if they were not involved in a research protocol (i.e. both types of blocks are performed routinely in clinical practice at Clements University Hospital and Zale Lipshy Hospital). As such, adjunct pain control using multimodal analgesia will be used to achieve adequate pain control. Preoperative gabapentin, acetaminophen or opiate medications as well as intraoperative opiates, ketamine, alpha-2-agonists, NSAID, acetaminophen or other analgesic may be used according to the standard of care multimodal analgesia practice. Postoperative adjuvant analgesics may include but is not limited to acetaminophen, NSAID, gabapentin, oral and IV opiate as needed, as well as opiate by IV patient controlled analgesia. For some types of surgery, concurrent sciatic nerve block may be desired and performed according to the anesthetic plan devised by the patient's faculty anesthesiologist in collaboration with the attending surgeon and patient wishes. To ensure appropriate completion of study protocol, the adductor canal block and all study procedures would occur before the sciatic block, which would still occur before surgery as is the standard of care. Those individuals who receive a sciatic block would have pain analyzed in a separate group from those receiving only an adductor canal block.

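### Pain is split by sciatic block received, a status set after randomization, and the plan does not say which pain result answers Hypothesis 2 or give an adjusted all-patient model

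*Combined protocol and SAP*

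**What the plan says.** Hypothesis 2 (Section 1) is that the two approaches give similar postoperative pain control, and Specific Aim 2 compares pain between the two randomized groups over the first 24 hours. Pain and opioid consumption are secondary endpoints; the endpoint list adds that pain is to be stratified by type of surgery.

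Section 3 allows a concurrent sciatic block for some types of surgery, under an anesthetic plan made by the anesthesiologist with the surgeon and the patient. On timing it says that "the adductor canal block and all study procedures would occur before the sciatic block". On analysis it says: "Those individuals who receive a sciatic block would have pain analyzed in a separate group".

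Section 14 says: "Pain scores and opiate consumption will also be analyzed in subgroups". The factors it lists are surgery location and type (foot, ankle, leg) and concurrent sciatic block. Knee surgery is eligible under Section 6 but is not in that list. Section 14 gives no pooled, adjusted or interaction model for pain or opioid use. No section says that the intended sciatic block is recorded before randomization, and no stratification factor is given for the randomization.

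**The concern.** There are two problems, and they should be kept apart.

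The first is which result counts. Section 3 reads as if patients with and without a sciatic block are analyzed only separately. Section 14 reads as if the subgroups accompany an overall comparison, which it never specifies. With several possible pain results and no order among them, the answer to Hypothesis 2 could be chosen after the data are seen.

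The second is how the sciatic groups are formed. Receipt is known only after randomization and after the sensory and strength tests. A comparison within groups formed that way is protected by randomization only if the arm has no influence on who enters them. Only the research assistant who times the block is described as blinded. The documents do not say that those who decide on the sciatic block are unaware of the arm or of the test results. If early block quality in one arm, together with a patient's proneness to pain, affected that decision, the arms within each sciatic group would no longer be alike.

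The pain and opioid conclusions are at stake. The sensory primary endpoint and MVIC are measured before the sciatic block and are not affected.

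**Working it through.** **The plan's own figure.** Section 14 sizes the study for the sensory score: "With an equivalence margin of 2 points", "assuming a standard deviation of 3 points", 70% power, 34 per group. For two one-sided t-tests (TOST) at 0.05 each and a true difference of 0, the smallest sufficient size is 34 per group, with 71.8% power (the normal approximation gives 33). The stated size is reproduced. It supplies the 34 per arm used below. It does not supply a pain SD or a pain margin; the documents give neither.

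**Group sizes.** Assume equal strata and no dropout, and take one factor at a time:
- sciatic block yes/no: 34/2 = 17 per arm
- three sites: 34/3 = 11.3 per arm
- four sites, if knee is added: 34/4 = 8.5 per arm

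**Precision.** The 95% CI half-width for a difference in means is t(0.975, 2n−2) × SD × √(2/n). The standard error relative to all patients is √(34/n). The pain SD is an assumption: 2.5 points as the working value, with 2 to 3 as a range.

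| Analysis | n per arm | t × √(2/n) | Half-width at SD 2.5 (SD 2 to 3) | SE ratio |
|---|---|---|---|---|
| All patients | 34 | 1.997 × 0.243 = 0.48 | 1.21 (0.97 to 1.45) | 1.00 |
| By sciatic block | 17 | 2.037 × 0.343 = 0.70 | 1.75 (1.40 to 2.10) | 1.41 |
| By three sites | 11.3 | 2.082 × 0.420 = 0.87 | 2.19 (1.75 to 2.62) | 1.73 |
| By four sites | 8.5 | 2.131 × 0.485 = 1.03 | 2.58 (2.07 to 3.10) | 2.00 |

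Unequal strata make the smaller one worse. If 20% received a sciatic block (assumed), that group would have 6.8 per arm and a half-width of 1.19 SD, or about 3.0 points at SD 2.5.

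One model in all 68 patients with treatment, sciatic plan and three-level site leaves 68 − 5 = 63 residual degrees of freedom. Its half-width is still 0.48 SD before any gain from the covariates.

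**Bias.** A simulation used 34 per arm, no direct effect of the arm on pain, and a sciatic block that lowers pain by 2 points. All of these effects are assumed.
- *Receipt follows a plan unrelated to arm.* Mean estimates are about 0 both within groups and in the adjusted model. The standard error is 0.98 to 1.00 within a group, 0.73 pooled without adjustment and 0.70 pooled with adjustment. Most of the gain comes from pooling.
- *Receipt depends on both arm and a pain-related trait.* The within-group estimates average −0.46. A pooled model adjusted for receipt also gives −0.46, so adjusting for receipt does not cure the problem. The all-patient estimate adjusted for plan is −0.43. It is not zero because in this scenario assignment changes sciatic use; it is the total effect of assignment, which randomization does identify. The −0.46 is neither that effect nor the direct effect, which is zero.

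This shows the mechanism. It does not estimate the bias in this trial.

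**The case against.** The strongest reply is that the sciatic block is part of the anesthetic plan and follows the type of surgery. Section 6 requires an anesthetic plan that already includes an adductor canal block, so a plan exists before enrollment. Section 3 says that care proceeds as it would outside the study, and it places the sciatic block last so that the study tests can be completed, not as a response to their results. On that reading receipt is in effect a baseline factor, and the split costs precision only. This largely stands: nothing in the documents shows that the arm influences receipt. What remains is that the sciatic part of the plan is nowhere said to be settled or recorded before randomization.

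It can also be said that Section 14 and Specific Aim 2 imply an overall comparison, so the subgroups need not replace it. That is a fair reading. But the overall analysis is not described, and Section 3 reads differently.

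Finally, pain is a secondary endpoint in a study that calls itself a pilot, and the choice between stratified summaries and a covariate model is partly preference. That stands, and it limits the weight of the point.

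**Conclusion.** The point holds as a cheap improvement to a secondary analysis. Sections 3 and 14 need reconciling, the main pain and opioid analysis needs naming, and the sciatic grouping should rest on a status fixed before randomization. Read one factor at a time, the separate analyses have standard errors 1.4 to 1.7 times that of the all-patient comparison: half-widths of about 1.75 to 2.2 points against 1.2. This assumes a pain SD of 2.5, equal strata and no dropout.

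A reader might infer four stronger things that the documents do not support:
- *That the plan leaves about 6 patients per arm per cell.* This requires crossing three sites with sciatic block (34/6 = 5.7), and Section 14 only lists the two factors.
- *That the randomized comparison is broken.* Bias is a possibility that the plan does not exclude, not something that it shows.
- *That splitting by surgery site is biased as well.* Site is a baseline factor, so that split costs precision only.
- *That any adjusted estimate would be unbiased.* That holds for adjustment on site and on planned sciatic block, not on the block received.

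**What to change.** - Before randomization, record planned sciatic block (yes/no) and surgery site, with knee as a category.
- In Section 14, make one model in all randomized patients the main analysis of pain and of opioid consumption: treatment + planned sciatic block + site. Say that this result answers Hypothesis 2 for pain.
- Show subgroups by planned, not received, sciatic block and by site as descriptive only.
- Change the sentence in Section 3 to match.

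The cost is one extra data field and two edited passages; sample size and clinical care do not change. The drawback is that some plans will change after randomization. Those patients stay in the category recorded beforehand, so planned status will predict pain somewhat less well than receipt would. Receipt should still be reported by arm, so that readers can see whether it differed.

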Hypothesis 1: The area of sensory blockade is different as a result of blockade at the mid-thigh and distal locations for the adductor canal block.

Specific Aim 1: To assess if the difference in cutaneous sensation to pinprick at 20-minutes after the block in patients randomized to receive mid-thigh or distal-thigh adductor canal blockades.

Hypothesis 2: To reconfirm that the mid-thigh and distal-thigh approaches to the ACB provide similar postoperative pain control for medial leg, medial ankle and medial foot surgery.

Specific Aim 2: To evaluate differences in the postoperative verbal response score in two randomized groups of patients received mid-thigh and distal-thigh adductor canal blockade in the first 24 hours postoperative.

Hypothesis 3: The maximum voluntary isometric contraction (MVIC) generated for knee extension is similar following the mid-thigh and distal thigh approaches to the ACB.

Specific Aim 3: To test the MVIC of knee extension with a hand held dynamometer at 20 minutes after the mid-thigh and distal-thigh approaches to the ACB.

Hypothesis 4: There is no difference in block performance time and patient satisfaction of two ACB techniques.

Specific Aim 4. To evaluate the differences in block performance time and patient satisfaction for two different ACB techniques.

Primary Endpoint:

- Distribution of cutaneous sensation to pinprick at 20-minutes and 30-minutes after the block.

Secondary Endpoints:

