Billing should be in accordance with standard practice and not paid for by the study, as all procedures are deemed standard of care. Patients will not be reimbursed for participation of the research.

Recorded Measures:

1. Baseline number of grid-points with full sensation.
2. The number of grid-points with a change in sensation at 20-minutes after the block to determine distribution of cutaneous sensory blockade.
3. Baseline ipsilateral quadriceps MVIC: 3 measurements of 5 seconds each separated by 30 seconds while seated with hip and knee at 90 degrees
4. MVIC at 20 minutes and 30 minutes as tested with same method as baseline test
5. Block performance time (needle in skin until needle out of skin)
6. Patient satisfaction for postoperative pain management
7. Pain scores on a 0-10 Likert scale at PACU (1-h) and at postoperative Day 1 (POD1) approximately 24 h following to surgery (0=no pain, 10=worse imaginary pain)
8. For inpatients, all recorded pain scores in the first 24 hours
9. Opioid consumption in PACU and for first 24 h

PHI including name, date of birth, MRN number, contact information including phone number will be recorded. Demographic information such as age, height, weight, BMI, race/ethnicity, and gender will be recorded. Medical and surgical history including allergies, pre-existing condition such diabetes, and medication list, ASA classification, type of anesthesia, laboratory results, regional anesthesia techniques, sensory mapping for adductor canal block, postoperative pain management, postoperative pain scores, and type of surgery will also be recorded.

4. Study Procedures:

- Potential subjects will be identified at the orthopedic presurgical clinic, the anesthesia preoperative clinic or the Day Surgery Unit. The electronic medical record (Epic) will also be used for prescreening potential subjects.
- Recruitment and consenting at Anesthesia preoperative clinics, Day Surgery Unit.
- Randomization: A computer generated randomization list will be used for randomization list.
 - **Anatomical landmarks at the knee joint:**

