 - Sensory blockade will be assessed over a grid area. The grid will be marked starting with anatomical landmarks at the knee joint: the medial inter-knee-joint point where the tibia meets the femur, the mid medial patella, the mid lateral patella, and along the same line at the semitendinosus tendon and 5cm posterior from that point. Then 5cm intervals will be plotted progressing cephalad to a total of 15 centimeters. This yields 20 grid points.
 - The study will use a 20 point-grid to standardize evaluation of sensory blockade in the anticipated border zone of block distribution. It will take approximately 1-2 minutes to make the grid and perform the testing. This is specifically for research purposes.
 - **Pinprick testing:**
 - The Sensory block for sharp sensations will be assessed by using Pinprick testing. Pinprick testing will be tested on a scale of 0-1, with 1 = normal sharp sensation and 0 = dull change of sensation, using a Neuropen for standardization of force.¹⁹⁻²¹
 - Sensation to the Neuropen will be performed gently across the skin with the end of the device to assess sharp touch. The subject will be asked to determine whether the stimulus feels sharp. The number of grid-points with a change in sensation from baseline will be recorded at 20-minutes and 30-minutes after the block.
 - Mechanical stimulation with pinprick testing is routinely used to test nociception in the bedside neurologic examination. Sharpness can be considered a surrogate for nociception because, whereas sharpness is not necessarily painful, mechanical thresholds for sharpness closely parallel those for pain.²⁶
 - **Maximum Voluntary Isometric Contraction:**
 - The MVIC will be assessed with a handheld dynamometer (Lafayette Instrument Company; Lafayette, Indiana).

- The patient will be in a seated position with the thigh parallel to the floor and the knee at a 90-degree angle with the feet off the floor. The dynamometer is applied to the leg 5 cm above the transmalleolar axis and perpendicular to the tibial crest. The patient is instructed to extend the leg at the knee with sustained maximal force for 5 seconds. This will be repeated 3 times with 30 seconds rest between each movement, and the force will be recorded. MVIC will be assessed at baseline and again at 20 minutes and 30 minutes post block.
 - **Adductor Canal Blockade:**

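### Baseline quadriceps MVIC is collected but no stated analysis uses it, so the Hypothesis 3 comparison would be less precise than the data allow

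*Combined protocol and SAP*

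**What the plan says.** Hypothesis 3 (Section 1) is a similarity statement: "The maximum voluntary isometric contraction (MVIC) generated for knee extension is similar following the mid-thigh and distal thigh approaches to the ACB". Specific Aim 3 gives the comparison as "To test the MVIC of knee extension with a hand held dynamometer at 20 minutes after the mid-thigh and distal-thigh approaches to the ACB", with no mention of baseline.

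The measurements are richer than the aim. Recorded Measures in Section 3 lists "Baseline ipsilateral quadriceps MVIC: 3 measurements of 5 seconds each separated by 30 seconds" (item 3) and "MVIC at 20 minutes and 30 minutes as tested with same method as baseline test" (item 4). Section 4, under Maximum Voluntary Isometric Contraction, repeats the schedule: "MVIC will be assessed at baseline and again at 20 minutes and 30 minutes post block". MVIC is the first secondary endpoint listed.

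Section 14 says "Data will be summarized as mean and standard deviation for continuous variables and frequency and percentages for categorical variables". It then plans TOST for the two blocking methods, with its only margin in points, and subgroup analyses of pain scores and opiate use. It does not mention MVIC, a change score, a covariate or a rule for summarising the three readings. The pinprick outcome is treated differently: Section 4 defines it relative to baseline.

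**The concern.** Knee-extension force can be expected to vary a good deal between patients before any block. Eligibility covers adults of either sex, a body mass index up to 50, and foot, ankle, leg or knee surgery. If the groups are compared on 20-minute values alone, that between-patient spread stays in the error term, although a baseline that could remove part of it has been measured.

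Precision matters more than usual here because Hypothesis 3 asserts similarity. Support for similarity comes from a narrow interval around zero. A non-significant difference from a noisy comparison does not provide it, yet is easily read as if it did. Leaving the model open also means that raw, change-score and adjusted results would all be available once the data are seen.

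**Working it through.** **Inputs from the documents.** n = 34 per group; equivalence margin 2 points; SD 3 points; alpha 0.05; power 70% (all Section 14, and all for the primary score in points). MVIC at baseline, 20 and 30 minutes (Sections 3 and 4).

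**Not in the documents.** The MVIC SD, an MVIC margin, and the baseline/post-block correlation rho. Rho is therefore an assumption, shown from 0.3 to 0.8.

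**Step 1: the plan's own figure.** For TOST with true difference 0, SE = 3 × √(2/34) = 0.728. The normal approximation to power at 5% per side is 2Φ(2/0.728 − 1.645) − 1 = 73.0%. The t-based calculation with 66 df gives 71.8%, and 34 is the smallest group size that reaches 70%. The stated figure reproduces. It concerns the score in points and says nothing about MVIC.

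**Step 2: variance of the MVIC group difference.** Take a post-only comparison as 1.
- ANCOVA on baseline: 1 − rho².
- Change from baseline, assuming equal SDs before and after the block: 2(1 − rho).
- ANCOVA relative to change: (1 − rho²) / [2(1 − rho)] = (1 + rho)/2.
- Post-only group size with the same precision as ANCOVA on 34: 34/(1 − rho²).

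| Assumed rho | ANCOVA vs post-only | Equivalent n per arm | Change vs post-only | ANCOVA vs change |
|---|---|---|---|---|
| 0.3 | 0.91 | 34/0.91 ≈ 37 | 1.40 | 0.65 |
| 0.5 | 0.75 | 34/0.75 ≈ 45 | 1.00 | 0.75 |
| 0.7 | 0.51 | 34/0.51 ≈ 67 | 0.60 | 0.85 |
| 0.8 | 0.36 | 34/0.36 ≈ 94 | 0.40 | 0.90 |

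**Step 3: width of the interval, in units of the post-block MVIC SD.** The unadjusted 90% half-width is t(0.95; 66 df) × √(2/34) = 0.405. With ANCOVA it is t(0.95; 65 df) × √[(2/34)(1 − rho²)] × √(1 + 1/64), where the last term allows for chance imbalance in baseline. This gives 0.389, 0.353, 0.291 and 0.245 at rho 0.3, 0.5, 0.7 and 0.8.

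**Reading the results.** A change score is not an equivalent remedy: it is less precise than ignoring baseline when rho is below 0.5. ANCOVA costs one degree of freedom and, through the 1/64 term, about 1.6% of variance, so it cannot be materially worse than the post-only comparison.

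**The case against.** The strongest reply is that the plan is silent on the MVIC model and does not choose an unadjusted one. Taking the baseline three times and repeating it by the same method suggests that some comparison with baseline was intended. This stands in part. Nothing in Section 14 rules out adjustment, and if the team meant change from baseline, the variance reduction from ANCOVA is 35% to 10% over the range shown, which at rho of 0.7 or 0.8 is well short of the gain over post-only values. But no such analysis is defined, and Aim 3 as written refers to post-block values alone.

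A reader might go further and infer that, with 34 per arm, the unadjusted interval is too wide to support or refute Hypothesis 3. The documents do not support that, because they give neither an SD nor a margin for MVIC. Purely as an illustration, borrowing the primary outcome's margin-to-SD ratio of 2/3 would give unadjusted TOST power of 71.8%, which meets the 70% the trial accepts for its primary comparison.

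A reader might also infer that the time point is left open, since 30-minute readings are taken as well. This is minor: Aim 3 and the Section 3 narrative both name 20 minutes, and an added measurement does not displace the stated one. Nor do the documents settle whether the mean or the best of the three readings should be used. Either is defensible if it is applied consistently.

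Finally, MVIC is secondary in what Section 3 calls a pilot study, and randomisation keeps an unadjusted comparison unbiased. Both are correct, and they limit the point to efficiency and pre-specification.

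**Conclusion.** The point holds as a gap in efficiency and pre-specification for a secondary endpoint. Baseline MVIC is planned for every patient, no stated analysis uses it, and the comparison implied by Aim 3 would give a wider interval than the collected data permit. The variance reduction against a post-only comparison runs from 9% at rho 0.3 to 64% at rho 0.8, so the gain could be slight or large. It rests on the assumed rho, on a linear relation with a common slope in both groups and, for the change-score comparison only, on equal SDs before and after the block. There is no bias, and the sample size and primary analysis are unaffected. Whether the unadjusted interval would be adequate for Hypothesis 3 cannot be judged from the documents.

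**What to change.** Add to Section 14:

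> MVIC at 20 minutes will be compared between groups by ANCOVA with treatment as factor and baseline MVIC as covariate, with the three readings summarised in the same way at each time. The adjusted difference will be reported with its confidence interval (90% if used for a TOST-type claim of similarity). The 30-minute MVIC is supportive, with the same model.

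State which summary of the three readings is used. If the trial intends to claim similarity of strength, it must also state and justify an MVIC margin before the data are seen; the 2-point margin in Section 14 does not carry over to a force measurement. Without a margin, report the adjusted estimate and interval and make no equivalence claim.

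The cost is a few sentences in Section 14, with no new data, visits or patients. Setting a margin is the only part that needs further thought.
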